1. INTRODUCTION

The present Statistical Analysis Plan extends the outcome analyses previously stated in the protocol version 2.0 (ClinicalTrials.gov Identifier: NCT03637036) to clarify how we will handle more analyses and a protocol deviation that occurred during the randomization process.

2. DATA

Data collection is described in protocol (version 2, page 5). However, deviations from the protocol resulted in modifications to some of the data we will have available for the analyses. Table 1 describes the data contained in the data file.

The first deviation occurred because of the four worksites originally planned to be in the trial, three could not take part. This left one worksite in the trial, i.e. Queen Elizabeth Hospital.

The second deviation affects our plans for sub-group analyses. This occurred because the trust records describe job roles differently than stated in the protocol. So instead of the job roles stated in the protocol, staff were stratified by two Employment-Types and four Job-Types.

The third deviation occurred as 898 (10.6%) of the hospital's 8438 staff randomized were allocated to a fifth, no-letter, control group. The remaining 7,540 staff were randomized to the planned four groups in equal numbers (i.e., 1885 participants to each of four groups). We will analyse data in the four groups per the original protocol and this will be the primary analysis. However, we will also carry out a subsidiary analysis to compare the results of this no-letter control group to the letter groups, as described in the below section titled 'Supplementary Analysis'.

Table 1. Data in the project analysis file

Type	Name	Codes
Intervention	Group Number	0 = Standard, 1 = Social Norms, 2 = Authority 3 = Combined, and 4 = No Letter Control
Demographics	Gender	0 = Female, and 1 = Male
	Type of Employment	0 = Bank, and 1 = Substantive
	Job Type	0 = Healthcare assistants and other support staff, 1 = Medical and dental staff, 2 = Nursing, midwifery and health visiting staff, and 3 = Scientific, therapeutic and technical staff (for the analyses, groups 0 and 3 will be combined)
Primary Outcome	Date of vaccination at Trust	DD-MM-YYYY, or blank if the vaccination was never received
Other outcomes (formally self-reported)	Refusal to take up the Vaccination	0 = No, and 1 = Yes
	Vaccinating at a non-trust location	0 = No, and 1 = Yes

3. ANALYSIS OBJECTIVES

- Objective 1 is to assess the effects of the two intervention types (Social Norms and Authority) and any interaction effect of these interventions on the on-site vaccination rates by the end of the trial, i.e. 4th of January 2019.
- Objective 2 is to assess the effects of the interventions on subgroups of the study. We are most interested in comparisons across the above stated three job types, though we will also compare the effects across genders. We will not examine the type of employment because the bank sub-group is small, but we will report the proportion of staff taking up the vaccine in this subgroup.
- Objective 3 is to assess cumulative rates of vaccinations across each group by week from the beginning to the end of the study period.

4. GENERAL ANALYSIS CONVENTIONS

All descriptive statistics will be reported with 95% confidence intervals, and statistical analyses will be two-sided.

5. ANALYSES

Our primary analysis will be a binary logistic regression analysis with on-site vaccination (0=No, 1=Yes) as the outcome variable and the two main intervention effects, Social Norms (0=No, 1=Yes) and Authority (0=No, 1=Yes), and the interaction effect as explanatory variables. The no-letter control group will not be considered in this primary analysis.

Descriptively, a table (Table 2), will be created displaying the staff vaccination uptake for each group with the corresponding exact binomial 95% confidence interval.

Table 2. Staff onsite vaccination rates

[figure not shown]
	Standard Group		Norms Group		Authority Group		Combination Group	
	n	Uptake Proportion (95% Confidence Interval)	n	Uptake Proportion (95% Confidence Interval)	n	Uptake Proportion (95% Confidence Interval)	n	Uptake Proportion (95% Confidence Interval)
Total	#	0.   (0.   , 0.  )	#	0.   (0.   , 0.  )	#	0.   (0.   , 0.  )	#	0.   (0.   , 0.  )
Gender								
Female	#	0.   (0.   , 0.  )	#	0.   (0.   , 0.  )	#	0.   (0.   , 0.  )	#	0.   (0.   , 0.  )
Male	#	0.   (0.   , 0.  )	#	0.   (0.   , 0.  )	#	0.   (0.   , 0.  )	#	0.   (0.   , 0.  )
Employment-Type								
Bank	#	0.   (0.   , 0.  )	#	0.   (0.   , 0.  )	#	0.   (0.   , 0.  )	#	0.   (0.   , 0.  )
Substantive	#	0.   (0.   , 0.  )	#	0.   (0.   , 0.  )	#	0.   (0.   , 0.  )	#	0.   (0.   , 0.  )
Job-Type								
Medical and dental staff	#	0.   (0.   , 0.  )	#	0.   (0.   , 0.  )	#	0.   (0.   , 0.  )	#	0.   (0.   , 0.  )
Nursing, midwifery and health visiting staff	#	0.   (0.   , 0.  )	#	0.   (0.   , 0.  )	#	0.   (0.   , 0.  )	#	0.   (0.   , 0.  )
Healthcare assistants, other support staff Scientific, therapeutic and technical staff	#	0.   (0.   , 0.  )	#	0.   (0.   , 0.  )	#	0.   (0.   , 0.  )	#	0.   (0.   , 0.  )

In addition to the primary analysis, a binary logistic regression analysis will be used to predict staff on-site vaccination rate (0 = No, 1= Yes) using all of the following variables: the two main intervention effects (Social Norms and Authority) and their interaction effect, Employment-type (0=Bank, 1=Substantive), Job-Type (1=Medical and dental staff, 2=Nursing, midwifery and health visiting staff, and 4= a combined group composed of Healthcare assistants, other support staff and Scientific, therapeutic and technical staff), Gender (0=Female, 1=Male) and any of the following interactions that are significant: Social Norms x Job type; Social Norms x Gender; Authority x Job type; Authority x Gender; Social Norms x Authority x Job type; and Social Norms x Authority x Gender. (If either of the three-way interactions is included, all the constituent two-way interactions will also be included.)

Figure 1. Time series chart

To achieve Objective 3, secondary analysis will assess the effects of the interventions over time, to examine the hypothesis that the benefits of the interventions may be greater nearer the beginning of the trial than nearer the end.

This effect will initially be assessed by visually examining a time-series chart, such as represented in Figure 1. We will also estimate the time to vaccination within each group to reach 70% vaccination. To do so, Kaplan–Meier rates of survival (i.e. non-vaccination) will be derived, with confidence intervals based on the exponential Greenwood formulation of the standard error. We selected 70% because this was the vaccination target and was achieved by the hospital over the 2017–2018 vaccination season. If a rate of 70% is not achieved in all four groups we will estimate the time to reach 10m%, where m is the largest integer such that the rate in all four groups is at least 10m%. The proportional hazards assumption will be tested by including interactions of each term (the two main intervention effects and their interaction) with log of time since 00:00 on 4th October 2018 in a Cox proportional hazards model.

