Primary: Will the content of different wording on the letters requesting NHS staff to receive the seasonal influenza vaccination affect the rate at which those staff are vaccinated?

Secondary: Will the effect sizes vary across different demographics?

Data/Outcomes.

- Staff IDs- this is needed to randomize and send letters-Will be deleted after data collection ceases
- Staff Name-this is needed to address letters, e.g., “Dear [name]” -Will be deleted after data collection ceases
- Group Number (e.g., 0=letter version one, 1=letter version two, 2=)
- Date of Vaccination at Trust (DD-MM-YYYY, or blank if the vaccination was never received),
- Indicating Refusal to take up the vaccination (0=No, 1=Yes),
- Indicating Vaccinating at non-Trust Location, e.g., general practice (0=No, 1=Yes)

There are no secondary outcome measures, but information related to the participants’ worksite, job role and gender will be used as predictors in the secondary analyses.

- Worksite (0=Queen Elizabeth, 1=Heartlands, 2=Solihull, 3=Good Hope),
- Job role (1=Doctor, 2=Nurse, 3=Other-frontline), 4=Other-non-frontline),
- Gender (0=Female, 1=Male, 2=Not indicated).

Data retrieval will be facilitated by UHB’s Clinical Business Development Lead from UHB's MyFluJab database, and from Occupational Health data systems.

Analyses.

The primary analysis will compare the proportions of staff that take up the vaccination in each group, where each group receives a different letter. The rates of vaccination will be analyzed with a binary logistic regression model including an interaction term and the two main effects. While all forms of wording will encourage uptake, we hypothesise that some will work better than others.

The secondary analysis will look for differences in the letter wording effectiveness related to sub-group demographics, i.e., worksite, job roles, and gender.

Analyses will be conducted by a UHB statistician according to UHB’s secure protocols.

Short Title: An improvement project around staffs' influenza vaccine uptake

Summary of main issues.

No significant ethical, legal, or management issues arise from this study.

The largest risk of this study is the opportunity for NHS staff data to be leaked. To minimize this risk, no individual-level data will be transferred across organizations. Rather all data will be retrieved and analyzed by authorized UHB staff.

Scientific Justification.

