- (6) Date vaccination was received at Trust, if ever,

Version 2.0

7 September 2018.

of 15

Short Title: An improvement project around staffs' influenza vaccine uptake

- (7) Whether the staff member indicated not intending to take up vaccination, and
- (8) Whether the staff member has indicated receiving the vaccination from another source, e.g., general practice.

UHB's statistician will analyze the data and then interpret the findings with UoW's researchers. UoW's researchers will write-up the findings for publication.

Randomization Process.

Yes.

Each NHS staff member will be randomized to one of the available groups, and each group will receive a different letter.

The randomization will be stratified by worksite and job role. The random number function RAND in Microsoft Excel will be used to generate random numbers and within each of the 12 strata the 25% of staff with the lowest values will be assigned to group 1, etc.

Participants.

Samples Size: Up to 18,000

How was the sample size decided? UHB aims to vaccinate approximately 18,000 NHS staff. The following sample-size calculations were performed (using an assumed alpha rate of 0.05 and a beta of 0.8) for a binary logistic regression model including an interaction term as well as two main effects.

To detect an interaction such that the uptake is 40% in three of the groups and 50% in the other group will require a sample-size of at least 750 per group. Thus, we have a sufficient sample size to find a much smaller difference overall and differences in sub-groups.

[figure not shown]
Inclusion: All UHB staff eligible for the seasonal influenza vaccination are eligible for this study.

Exclusion: No patients will be excluded.

Duration in study: NHS staff will be monitored in this study for approximately 4 months, i.e., from the date the letter is disseminated (near the end of September) through the 4th of January 2019. Note that our observations only involve recording when NHS staff receive the vaccination, and such data are already routinely recorded.

Risks: There are no risks beyond standard practice. The largest risk regards NHS staff's personal data being leaked. To minimize the risk of data leaks, no data will be transferred across organizations. Rather data will be retrieved and analyzed by authorized UHB staff according to UHB's standard protocols.

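### The primary model omits both stratification factors, and the only adjusted factorial model takes a form that depends on the data

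*Combined protocol and SAP*

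**What the plan says.** - **Randomisation.** The SAP (Section 2, second deviation) reports that "staff were stratified by two Employment-Types and four Job-Types", which makes eight strata at the one remaining site. The third deviation gives only group totals: "1885 participants to each of four groups". The protocol (Randomization Process) planned that "within each of the 12 strata the 25% of staff with the lowest values will be assigned to group 1", and so on for the other groups.
- **Primary model.** SAP Section 5: "Our primary analysis will be a binary logistic regression analysis with on-site vaccination (0=No, 1=Yes) as the outcome variable". The explanatory variables are Social Norms, Authority and their interaction. This is the model in the protocol's Analyses section, which begins "The primary analysis will compare the proportions of staff that take up the vaccination in each group". Neither document gives a reason for leaving the strata out.
- **Adjusted factorial model.** SAP Section 5 adds a second logistic model that always contains Employment-Type, Job-Type and Gender, together with "any of the following interactions that are significant", drawn from six candidates (four two-way, two three-way). No significance level, test or order of selection is given. Job-Type has three levels here, because SAP Table 1 says "for the analyses, groups 0 and 3 will be combined".
- **Other adjusted model.** The model in SAP Section 9 is also adjusted, but its exposure is letter versus no letter.

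**The concern.** An analysis normally reflects the factors used to restrict the randomisation. If uptake differs between strata and allocation was balanced within them, the unadjusted model-based standard error is slightly larger than the true sampling variability. Tests are then a little conservative and some power is lost.

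The SAP does offer an adjusted factorial model, but its final form is settled by significance tests on the trial data. If an interaction with job type or gender is kept, the affected letter coefficients stop being overall effects and become effects in a reference category. The SAP therefore contains no factorial analysis that both matches the randomisation and has a fixed form.

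**Working it through.** **1. The plan's own sample size.** The protocol plans for an interaction in which "uptake is 40% in three of the groups and 50% in the other group", with alpha 0.05 (two-sided, SAP Section 4) and power 0.8, and states at least 750 per group.

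- Risk-difference scale: n = (3×0.24 + 0.25)(1.96 + 0.8416)²/0.10² = 762.
- Log-odds scale: n = (3/0.24 + 1/0.25)(1.96 + 0.8416)²/(ln 1.5)² = 788.

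The stated figure reproduces closely. At 1,885 per group the log-odds power is Φ(0.4055/√(16.5/1885) − 1.96) = 99.1%.

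**2. Cost of omitting the strata.** The documents give no stratum sizes or uptakes, so these are assumptions: job-type weights 20/40/30/10%, bank share 5% with log-odds lower by 1, and all eight strata shifted on the logit scale to a mean p̄ of 71.6% (QEHB last winter, protocol Appendix 1). Job-type uptakes before shifting are A 65/60/60/55%, B 75/60/60/50% and C 80/65/50/30%. With stratum weights w and uptakes p, for the interaction log odds ratio:

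- R² = Σw(p − p̄)²/[p̄(1 − p̄)]
- Unadjusted SE = √(4/[n p̄(1 − p̄)]) = √(4/[1885×0.716×0.284]) = 0.1022
- True SD under within-stratum balance = √(4Σwp(1 − p)/{n[p̄(1 − p̄)]²})
- Null rejection = 2[1 − Φ(1.96×SE/SD)]

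For C, Σwp(1 − p) = 0.1854, so SD = √(4×0.1854/[1885×0.2033²]) = 0.0975.

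| | A | B | C |
|---|---|---|---|
| R² | 1.5% | 3.0% | 8.8% |
| True SD | 0.1014 | 0.1006 | 0.0975 |
| SE excess over SD | 0.8% | 1.5% | 4.7% |
| Null rejection | 4.8% | 4.7% | 4.0% |
| Adjusted power where unadjusted is 80.0% | 80.4% | 80.8% | 82.3% |

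Simulated power with balanced strata (unadjusted, three-level Job-Type, four-level Job-Type; Gender left out):

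- C (20,000 runs): 80.1%, 81.7%, 82.2%.
- B: 79.7%, 80.3%, 80.3%.

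**3. Sensitivity to the assumptions.**

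- Bank share 2–10% with a log-odds shift from 0 to −2: the gain runs from 0.1 to 4.2 points.
- Equal job-type weights and stratum uptakes from 14% to 92%: 4.8 points, the largest found in this set.
- A separate simulation at about 46–48% uptake with strong stratum differences (job types 30–75%, bank log-odds −1.5): power 69.6% unadjusted, 73.2% with three levels and 74.3% with four. Unadjusted null rejection was 3.1–3.6%.
- The protocol's 40/40/40/50% effect: a gain of at most about 0.2 points.
- Pattern C without balance within strata: unadjusted null rejection 4.9%, so no conservatism. Power was 78.8% unadjusted and 82.2% with four levels.

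**4. The selection rule.** Take each candidate as tested at 5% (assumed) with no true effect modification. Six independent tests would keep at least one in 1 − 0.95⁶ = 26.5% of trials. Simulations that respect the hierarchy, under different assumed strata, gave 26.1% to 29.8%.

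The null Social Norms coefficient was rejected after selection in 8.2% of trials, against 5.2% for the fixed main-effects model. A second simulation gave 8.4% against 5.4%, and a smaller one (1,500 runs) 6.0% against 4.1%. The exact size depends on selection details that the SAP leaves open; the direction is the same each time.

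**The case against.** The strongest reply is that nothing here is an error. The primary model is the registered one, it is fully pre-specified, and its odds ratio is a valid marginal effect that fits the protocol's comparison of proportions. After several deviations, keeping it is defensible. The gains in power rest on assumed stratum uptakes and on shrinking the effect until unadjusted power is 80%. The conservatism needs within-stratum balance, which the SAP does not document. The additional model already supplies most of the adjustment: 1.6 of 2.1 points in pattern C and the whole gain in pattern B. The interaction selection serves the subgroup objective and does not touch the primary result.

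Most of this stands. The primary analysis does not have to change, and the gain in power alone would be a weak reason to change it. What the reply leaves unanswered is that the additional model is the only adjusted factorial analysis, that its meaning can change with the data, and that it does not use the job types as randomised.

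**Conclusion.** The point holds as a minor, optional improvement. For the primary model there is no bias and no type I error inflation. The loss of power is under 1 point with small or moderate stratum differences, about 2 points in the large central case, and up to about 5 points only in strong scenarios. All of these figures rest on assumed stratum sizes and uptakes, and the conservatism also rests on balance within strata.

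The absence of inflation does not extend to the selected model. There, a spurious interaction enters in roughly a quarter to three tenths of null trials at an assumed 5% level, and the letter coefficient is rejected more often than in the fixed model.

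**What to change.** Before the statistician receives the outcome data (SAP Section 6), name one model: Social Norms, Authority, their interaction, Employment-Type (two levels) and Job-Type (all four randomised levels) as fixed main effects, with no terms chosen by significance. Either make it primary, with the unadjusted registered model as the sensitivity analysis, or keep the registered model as primary and name this one as the sensitivity analysis. The second route is enough to close the gap.

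Report all six interaction tests for the subgroup objective instead of selecting among them, and merge job types 0 and 3 only for subgroup analyses and display.

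With 0/1 coding, each letter coefficient is the effect when the other factor is absent, in the plan's model and in this one. Alongside the conditional odds ratios, therefore, give standardised risk differences for each factor averaged over the other, and for the interaction, with standard errors that respect the stratification. At 71.6% uptake, and before any adjustment, the SE of a letter effect is √(2×0.716×0.284/1885) = 1.47 points with the other factor absent and √(2×0.716×0.284/3770) = 1.04 points when averaged.

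The cost is a few lines in the SAP and four extra parameters on a four-parameter model with 7,540 staff, using variables already in the analysis file. If the adjusted model becomes primary, the departure from the protocol's Analyses section must be recorded. As a sensitivity analysis it changes nothing registered.

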This research is worth doing because current vaccination rates among NHS staff remain lower than desired. The variation among NHS trusts' vaccination rates (from less than 40% to more than 80%)⁶ suggests that some trusts' may doing something better. Unfortunately, reviews of past data do not easily indicate malleable factors as to why the rates differ. The current study will examine one malleable factor that may affect uptake rates, i.e., the content of letters asking staff to vaccinate.

Design and methodology.

Null Hypothesis: All the letters will similarly influence the rate at which staff take up the vaccination.

Alt Hypothesis: The letters will differently influence the rate at which staff take up the vaccination.

The RCT method was selected, because it is the most robust method through which to make causal inferences. The RCT method is feasible, because UHB already monitors whether each staff member receives the vaccination.

There will be no 'no-treatment' control group. All letters will non-coercively invite NHS staff to take up the vaccination, though we expect some reminders to work better than others.

Letter wordings are given Appendix A. One factor will emphasize an authority figure inviting staff to vaccinate. The other factor will emphasize a competitive social norm describing peer hospital performance. Letters will be sent both by e-mail and through the internal post.

UHB's Clinical Business Development Lead will send UHB's statistician a data file in mid-September containing information about staff who should be invited to have a vaccination:

- (1) IDs-needed to randomize at an individual level
- (2) Staff Name-needed to address reminders, e.g., "Dear [name]"
- (3) Worksites-needed to stratify randomization, and
- (4) Job Roles-needed to stratify randomization.

We expect this file to include up to 18,000 NHS staff members, and this number is more than sufficient for our primary comparison. UHB's statistician will randomize these staff to receive one of the letters and then will help UHB's communications team to disseminate the letters according to the randomized schedule.

In January UHB's Clinical Business Development Lead will send UHB's statistician a data file describing whether those staff randomized to receive a letter went on to get vaccinated by the 4th of January. The data will contain information describing each staff member's:

- (1) ID,
- (2) Worksite,
- (3) Job Role,
- (4) Gender,
- (5) Group,

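### As most naturally read, the primary model's two main intervention effects are single-letter-versus-Standard contrasts, and no effect of either factor averaged over the other is planned

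*Combined protocol and SAP*

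**What the plan says.** The trial is a 2 × 2 factorial of letters: Standard, Social Norms, Authority and Combined, with "1885 participants to each of four groups" (SAP section 2).

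- **Objective (SAP section 3).** "Objective 1 is to assess the effects of the two intervention types (Social Norms and Authority) and any interaction effect of these interventions", on on-site vaccination by 4 January 2019.
- **Primary model (SAP section 5).** A binary logistic regression with "the two main intervention effects, Social Norms (0=No, 1=Yes) and Authority (0=No, 1=Yes), and the interaction effect as explanatory variables". The no-letter group is left out.
- **Adjusted model (SAP section 5).** The same label, "the two main intervention effects (Social Norms and Authority) and their interaction effect", with employment type, job type, gender and any significant interactions of the factors with job type or gender.
- **Protocol, Analyses.** The primary analysis will "compare the proportions of staff that take up the vaccination in each group, where each group receives a different letter", using "a binary logistic regression model including an interaction term and the two main effects".
- **Protocol, null hypothesis.** "All the letters will similarly influence the rate at which staff take up the vaccination".

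Table 2 gives uptake for the four letters separately. The only pooling across letters is any letter against no letter (SAP section 9), which is not a factor effect. No section describes a contrast averaged over the other factor, a model without the interaction, or how the two lower-order coefficients will be read.

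**The concern.** In a 2 × 2 factorial, the main effect of a factor usually means its effect averaged over the levels of the other factor. Once an interaction term is present and both factors are entered as 0/1, the lower-order coefficients no longer estimate that. Each is the effect of one factor where the other is absent, so the Combined letter contributes nothing to either.

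Two things are at stake. If the factors interact, the simple and averaged effects answer different questions and can differ materially, so a reader given the simple effect under the label of main effect may take it for the factor's overall effect. If the factors do not interact, both contrasts estimate the same quantity, and the plan would report only the less precise one as its answer for each intervention type.

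**Working it through.** **Inputs.** n = 1,885 per group, so 4 × 1,885 = 7,540 in all and 2 × 1,885 = 3,770 per two-letter comparison (SAP section 2). Two-sided tests (SAP section 4). Alpha 0.05, and power 0.80, which is how the printed beta of 0.8 must be read (protocol, Participants). Uptake of 40% in three groups and 50% in the fourth (same place). A 70% base as a second case, because SAP section 5 says that target was achieved in 2017–2018. The 3-point effect in step 4 is an assumption; the documents give no such figure.

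**1. The plan's own figure.** The protocol states at least 750 per group for the interaction. On the risk-difference scale, n = (1.96 + 0.842)² × (3 × 0.24 + 0.25) / 0.10² = 762 after rounding up. On the log-odds scale, n = (1.96 + 0.842)² × (3/0.24 + 1/0.25) / (ln 1.5)² = 788. Power at 750 is 79.4% and 78.0% respectively. The figure reproduces as a two-sided interaction test.

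**2. What the coefficients are.** Let L be a group's log-odds of uptake and v = 1/(n p q) its variance.

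- Social Norms coefficient (0/1) = L_Norms − L_Standard, with variance v_N + v_S.
- Authority coefficient (0/1) = L_Authority − L_Standard, with variance v_A + v_S.
- Interaction = L_C − L_N − L_A + L_S, with variance v_S + v_N + v_A + v_C.
- Averaged Norms effect = [(L_N − L_S) + (L_C − L_A)]/2 = Norms coefficient + half the interaction, with variance (v_S + v_N + v_A + v_C)/4. The averaged Authority effect is formed in the same way.

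**3. The protocol's scenario at n = 1,885.**

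Simple SE = √(2/(0.24 × 1,885)) = 0.066. Averaged SE = ½√((3/0.24 + 1/0.25)/1,885) = 0.047.

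- *Combined is the 50% group.* Both 0/1 coefficients are 0, so OR 1.00 (expected 95% CI 0.88 to 1.14). Each averaged effect is ½ ln 1.5 = 0.203, so OR 1.22 (1.12 to 1.34).
- *Norms is the 50% group.* The Authority coefficient is again 0, OR 1.00 (0.88 to 1.14). The averaged Authority effect is −½ ln 1.5 = −0.203, OR 0.82 (0.74 to 0.89).

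Fitting the first case with 0/1 and with −½, +½ codes gave the same interaction both times (0.405, SE 0.094).

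**4. Precision without interaction.** With equal uptake of 40%, SE is √(2/(0.24 × 1,885)) = 0.066 simple and √(1/(0.24 × 1,885)) = 0.047 averaged, a ratio of √2 ≈ 1.41. Power is Φ(|b|/SE − 1.96) + Φ(−|b|/SE − 1.96).

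| Base uptake | Power for a 3-point effect: simple | averaged | Smallest effect with 80% power: simple | averaged |
|---|---|---|---|---|
| 40% | 46% | 75% | 4.5 points | 3.2 points |
| 70% | 53% | 82% | 4.1 points | 2.9 points |

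At 40%, for example, b = logit 0.43 − logit 0.40 = 0.124, so b/SE is 1.87 simple and 2.64 averaged.

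**5. The order can reverse.** If the 3-point effect vanishes when the other factor is present, averaged power is 26% against 46% simple at a 40% base, and 31% against 53% at 70%.

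**6. Why reporting should be fixed in advance.** In a null simulation (4 million draws, equal variances), type I error per factor at nominal 5% was 5.0% if one contrast is fixed beforehand, 6.4% if the interaction test chooses between them, and 8.3% if whichever is significant is read.

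**The case against.** **The codes may be data codes only.** The SAP prints codes in the same style for the outcome, and job type appears as 1, 2 and 4, which cannot be design-matrix values for a nominal variable. If the software applied sum-to-zero contrasts, the printed terms would be averaged effects. A reader might infer that the terms are certainly mislabelled; the documents do not prove that. Direct 0/1 entry is the likelier reading, and under either reading the SAP does not say which contrast is meant.

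**Main effect is ordinary wording for a lower-order model term.** True, and no section says how the coefficients will be captioned. But Objective 1 is about the intervention types, and these terms are the only estimates planned for them.

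**Simple effects suit the protocol.** The protocol compares letter with letter, and its sample size targets the interaction. This stands: simple effects are a legitimate target, and the model need not change.

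**Averaging is not always better.** This also stands. Steps 3 and 5 show cases where the averaged effect misleads if read alone or has less power. A reader might infer that the averaged effect should replace the coefficients; the working does not support that.

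**Nothing is lost.** Any contrast can be recovered from the four groups. A reader might infer that the analysis is invalid, that data are discarded, or that type I error is inflated as planned. None of this follows: the 6.4% and 8.3% rates belong to selection rules that the SAP does not propose, and the sample-size figure is not affected.

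**Conclusion.** The point holds as a minor one about the estimand and its label. On the natural reading of the coding, the two terms offered as main intervention effects are Norms versus Standard and Authority versus Standard, each on half of the 7,540 staff, and no section plans the effect of either factor averaged over the other.

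The size depends on the truth. In the protocol's scenario the gap is OR 1.00 against 1.22 for each factor if Combined is the odd group, or 1.00 against 0.82 for Authority if Norms is. Without interaction there is no bias, only a standard error about 1.41 times larger than the same fit can give. The power figures rest on the assumed 3-point effect. The model fit, the interaction test and Table 2 are the same whichever contrast is named.

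**What to change.** In SAP section 5, keep the model and make these wording changes:

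- **Primary analysis.** Label the two 0/1 coefficients as the Norms letter versus Standard and the Authority letter versus Standard. State that each factor's averaged effect (coefficient plus half the interaction, from the same fit) is always reported with its 95% confidence interval beside the simple effects and the interaction, whatever the interaction test shows.
- **Adjusted model.** Use the same labels. If factor interactions with job type or gender enter, say that the coefficients, and the averages built from them, also apply to the reference job type and gender, and name those references.

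Which contrast should carry a test of each factor is a trade-off for the trial team. If a test is to be claimed, the choice should be written down before the data are seen.

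The cost is a few lines of text, with no change to data, allocation or fit. Two more estimates are reported, and under strong interaction the averaged effect must be read with the simple effects.
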